#### Secondary Effectiveness Endpoint

- Tremor power (kinematic response), as collected with the device during postural holds (outstretched or wing beating), change from pre-stimulation to post-stimulation across sessions.

This endpoint will be tested statistically using hypotheses as defined above.

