**PROSPECT: PROSPECTIVE STUDY FOR SYMPTOMATIC RELIEF OF
ESSENTIAL TREMOR WITH CALA THERAPY**

**PROTOCOL ET-14
REV A; 22 JUNE 2018**

Cala Health, Inc.
[name]
[name]

CLINICAL STUDY SYNOPSIS

| Study Objective | |
|------------------------|--|
| Title | PROSPECT: PROspective study for SymPtomatic relief of Essential tremor with Cala Therapy |
| Study Device | Cala TWO Device |
| Objective | The study objective is to evaluate symptomatic hand tremor relief in the treated hand following stimulation with the Cala TWO device in adults with essential tremor over a 3-month duration |

| Study Design Elements | |
|------------------------------|--|
| Study Design | Prospective, multi-center, single-arm, non-significant risk study designed to evaluate the Cala TWO device. Subjects will be screened for eligibility and fitted with a Cala TWO device. Subjects will wear the device at home for a period of 3 months, during which they will be asked to stimulate their dominant hand twice a day. The stimulation amplitude will be based on each subject's stimulation threshold. Subjects will have in clinic assessments at enrollment, month 1 and 3. |
| Effectiveness Endpoints | 
The effectiveness of the Cala TWO device in reducing essential tremor symptoms will be evaluated by the following:
 
Co-Primary Effectiveness Endpoints
 
 • TRG Essential Tremor Rating Assessment Scale (TETRAS) subset score, relevant to the stimulated upper limb, change from pre-stimulation at baseline to post-stimulation at 3 months. • Bain & Findley Activities of Daily Living (ADL) scale subset score, relevant to the stimulated upper limb, change from pre-stimulation at baseline to post-stimulation at 3 months. 
Secondary Effectiveness Endpoint
 
 • Tremor power, as collected with the device during postural holds, change from pre-stimulation to post-stimulation across sessions. 
Additional Exploratory Analyses
 
 • Quality of Life in Essential Tremor Questionnaire (QUEST) • Clinician/Patient Global Impression of Severity (C/PGI-S) • Clinician/Patient Global Impression of Improvement (C/PGI-I) • Patient Session Impression of Improvement (PSI-I) • TETRAS – subset relevant to non-stimulated upper limb • TETRAS and ADL pre- versus post-stimulation within each visit • Product Survey • Device usage metrics |

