## 2 STATISTICAL METHODS

### 2.1 General Principles

- All hypothesis testing will be performed using a two-sided test at a 0.05 level of significance or a one-sided test at a 0.025 level of significance. P-values will be rounded to three decimal places. If a p-value is less than 0.001 it will be reported as “< 0.001.”
- Summary statistics will be reported for all analyzed variables.
  - Continuous data will be summarized using descriptive statistics: mean, standard deviation, median, and interquartile range (first and third quartiles).
  - Categorical, non-ordered variables will be summarized using frequency counts and percentages.
  - Ordinal variables, including those specific to study outcomes – e.g., the TRG Essential Tremor Rating Assessment Scale (TETRAS) and the Bain & Findley Activities of Daily Living (ADL) scale -- will be summarized using measures of central tendency and variance as opposed to frequency counts and percentages; that is, these variables will be reported using the same metrics as defined above for continuous variables.
- For events which can occur more than once in a single subject (e.g., adverse events), the percentage will be based on subjects experiencing the event, and both subject and event counts will be reported.
- Baseline is defined as the last measurement for the outcome of interest obtained before the exposure to study treatment.
- For time-to-event analyses, complete dates for events of interest (e.g., index treatment, outcome events, censoring), will always be used. Incomplete dates will be incorporated by defining the event as occurring on the earliest date possible given the incomplete information. E.g., a date of UNK-FEB-2018 will be incorporated into the analysis as 01-FEB-2018.
- Statistical analyses will be performed in SAS (SAS Institute, Cary, N.C.) version 9.3 or later, R (R Foundation for Statistical Computing, Vienna, Austria) version 3.2 or later, Matlab (The MathWorks, Inc., Natick, MA) version R2016B or later, Python (Anaconda, Inc., Austin, TX) version 3.6.6 or later, or in another validated statistical software package.

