### 2.2 Analysis Populations

As stated in section 1.2, available data on all enrolled subjects will be summarized and reported, referred to in ICH E9 (“Statistical Principles for Clinical Trials”) as the *full analysis set*.

---

Two analysis populations will be defined, one consisting of all available data evaluated under ITT principles. For this purpose, “available data” means that missing data will not be replaced or imputed, and that endpoints defined as change scores (e.g., the co-primary endpoints) require both baseline and follow-up data to be present to be included in analyses.

For the ITT population, consented subjects who withdraw consent prior to device assignment, or who are found not to meet the inclusion/exclusion criteria prior to device assignment (e.g. not enrolled) will not be included in the intent-to-treat (ITT) population.

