### **2.3 Co-Primary Endpoints**

Two co-primary endpoints are defined: dominant hand (DH) upper-limb performance on the TRG Essential Tremor Rating Assessment Scale (TETRAS), and the Bain & Findley Activities of Daily Living (ADL) scale. Statistical testing of each primary endpoint will be based on the cohort of all enrolled and treated subjects for whom outcome data are available.

The statistical objective related to each primary endpoint is to demonstrate that essential tremor is reduced from baseline under treatment with the Cala TWO device. Formally, the null and alternative hypotheses to be tested for each primary endpoint are as follows:

$$\begin{aligned} H_0: \mu_T &\geq 0 \\ H_A: \mu_T &< 0 \end{aligned}$$

where  $\mu_T$  is the raw change in the rating score from pre-stimulation at baseline to post-stimulation at three months in the endpoint in question.

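### Does the tremor-power endpoint need its own pairing rule and a stated unit of analysis?

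*SAP*

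**What the plan says.** SAP 2.7 defines the secondary endpoint as tremor power "as collected with the device during postural holds (outstretched or wing beating), change from pre-stimulation to post-stimulation across sessions", and adds "This endpoint will be tested statistically using hypotheses as defined above". The protocol synopsis defines the endpoint in nearly the same terms and gives no more detail.

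The hypotheses referred to are in SAP 2.3, introduced as the "null and alternative hypotheses to be tested for each primary endpoint". Their parameter "is the raw change in the rating score from pre-stimulation at baseline to post-stimulation at three months in the endpoint in question"; the null is a value of zero or more, the alternative a value below zero. SAP 2.1 sets the level at one-sided 0.025 or two-sided 0.05.

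Two general rules also bear on the endpoint. SAP 2.2 says that "endpoints defined as change scores (e.g., the co-primary endpoints) require both baseline and follow-up data to be present to be included in analyses". SAP 2.1 says "Baseline is defined as the last measurement for the outcome of interest obtained before the exposure to study treatment". SAP 2.2 describes an analysis population "one consisting of all available data evaluated under ITT principles", and SAP 2.9 adds that missing values are not routinely imputed.

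**The concern.** Two things appear not to fit.

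**Inclusion.** The rule in 2.2 names the co-primaries only as an example, so it seems to cover tremor power. Baseline under 2.1 looks like one value per subject, taken before the first stimulation, yet every later pre-stimulation reading comes after exposure. Read literally, a subject whose first reading is missing would be dropped despite having many complete sessions, while nothing would require both readings in a later session.

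**Combination and unit.** Stimulation is requested twice a day for about three months, so each subject contributes a long series. Neither document says how sessions are averaged, how outstretched and wing-beating holds are merged, or whether the subject or the session is the unit. A mean weighted by session and a mean of subject values both fit the wording, and they differ if subjects who benefit more also use the device more.

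At stake is the only primary or secondary effectiveness endpoint that is collected by the device, in a study without a control arm.

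**Working it through.** The documents give no sample-size, variance or effect figure, so there is no planned number to reproduce. Missing rates, ICCs, session counts and correlations below are assumptions.

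**Scheduled sessions.** Two per day (SAP 1.1) over 3 months ± 2 weeks (synopsis), taking 3 months as 90 days: 2 × 76 = 152 to 2 × 104 = 208.

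**Inclusion rule, text against text.** SAP 2.7 sets the contrast for tremor power and does not use the word baseline. SAP 2.2 is a completeness rule and does not redefine that contrast. Its evident purpose is that both parts of a change must exist. For this endpoint the parts are a session's pre and post readings. With no routine imputation, a session lacking either one yields no change score, so both are needed without a further rule.

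**Inclusion rule, size under the literal reading.** With N = 500 (the cap) and p the chance that a reading is missing:
- Loss under a single first-reading baseline = 500p. For p = 0.02, 0.05, 0.10, 0.20 this is 10, 25, 50, 100 subjects.
- Loss when one complete session among m suffices = 500 × (1 − (1 − p)²)^m. At p = 0.20, 1 − 0.8² = 0.36; m = 5 gives 3.0 subjects and m = 10 gives 0.02.

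The first line is only the cap times an assumed rate. The second assumes that missing readings are independent across a subject's sessions; a failed or unused device would break that and narrow the difference.

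**Weighting.** If count correlates r with benefit, a session-weighted mean shifts from the subject mean by r × CV of the counts, in between-subject SDs.
- Counts uniform on 90-180: CV 0.19, shift 0.02-0.06 for r = 0.1-0.3.
- Counts uniform on 10-180: CV 0.52, shift 0.05-0.16.

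Simulated rejection at one-sided 0.025 with true mean change zero (N 100-500, ICC 0.01-0.4, 4,000 replicates):

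| Analysis | r = 0 | r = 0.1-0.3, 90-180 sessions | r = 0.1-0.3, 10-180 sessions |
|---|---|---|---|
| Session-weighted, subject-clustered SE | 0.021-0.030 | 0.039-0.236 | 0.052-0.874 |
| Random-intercept weights | 0.020-0.028 | 0.021-0.063 | 0.023-0.302 |
| One value per subject, t-test | 0.021-0.030 | 0.021-0.030 | 0.021-0.030 |

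The value near 0.87 needs N = 500, ICC 0.4, counts of 10-180, r = 0.3 and a mean of exactly zero, all at once. With a true benefit of 0.5 between-subject SD (counts 10-180, ICC 0.4, N 100-500), both the session-weighted and the per-subject test reject in at least 0.99.

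**Price of fixing equal subject weights.** The variance of a subject mean over n sessions is proportional to v = ICC + (1 − ICC)/n. The SE of equal weights over that of optimal weights is √(mean of v × mean of 1/v):
- counts 10-180: about 1.10 at ICC 0.01, 1.01 at 0.1, 1.00 at 0.4;
- counts 1-180, if subjects with a single session are admitted: 1.34 at ICC 0.01, 1.05 at 0.1, 1.00 at 0.4.

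**The case for a change.** The strongest case for a change is pre-specification. A tested endpoint should have its estimate fixed before data are seen, and 152-208 scheduled sessions per subject make the combination rule part of that estimate. A few sentences would settle it and no new data are needed. There is also a worse possibility: an analyst could treat sessions as independent. With 180 sessions the design effect is 1 + 179 × ICC, that is 2.79 at ICC 0.01 and 90.5 at ICC 0.5. The true one-sided error would then be 1 − Φ(1.96/√2.79) = 0.12 up to 1 − Φ(1.96/√90.5) = 0.42.

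The omission stands: the combination rule and the unit are not written down. The rest carries less weight. The SAP does not propose to treat sessions as independent. Its analysis sets consist of subjects, the hypotheses in 2.3 are tested on a cohort of subjects, and 2.1 bases percentages for recurrent events on subjects; the natural carry-over is one value per subject or a subject effect. Both weightings compared above respect clustering, and the session-weighted rejection rates are not errors for that analysis's own target, the average session. The protocol lists "Device usage metrics" among the exploratory analyses, so data on how far use varied should be available when the result is read. Requiring a raw scale, a t-test and equal subject weights would go beyond the text, which says raw change for the co-primaries but only change for tremor power.

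**Conclusion.** No change to the plan is called for. The mismatch with 2.2 is one of wording: it bites only if a once-per-subject baseline is forced on an endpoint whose own definition pairs readings around stimulation, and the loss of 10-100 of 500 subjects rests wholly on assumed missing rates of 2-20%.

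The missing combination rule is a gap that competent analysts fill soundly, by a subject summary or a model with a subject effect. Which one to use is a trade-off. Equal subject weights hold 0.021-0.030 under the null even when use tracks benefit, but cost up to 1.34 times the optimal SE if ICC is 0.01 and some subjects have very few sessions. Other weightings recover precision but move toward the heavier users. The two can disagree near a zero effect when use and benefit are correlated; at a benefit of 0.5 SD and ICC 0.4 they do not.

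The endpoint is secondary. The co-primary tests, the direction and the significance level are unaffected. The conclusion assumes that the analysis respects clustering by subject, which nothing in the SAP contradicts. The protocol supplied is a synopsis, so a fuller description of the device readings may exist elsewhere.

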### **2.8 Safety Outcomes**

The safety of the Cala TWO device will be evaluated by the incidence of device and therapy-related adverse events. Additionally, all adverse events documented during study conduct will be tabulated and reported.

### **2.9 Missing Data**

The primary analysis cohort will be the full analysis set as defined above. Missing data will not routinely be replaced or otherwise imputed.
